4.3.2 Dosage, Administration, and Compliance

Atezolizumab and BCG are investigational medicinal products (IMPs) in this study.

4.3.2.1 Atezolizumab

The dose level of atezolizumab in this study is 1200 mg administered by IV infusion q3w. There will be no dose reduction of atezolizumab.

Cohort 1A: Patients receive atezolizumab 1200 mg IV q3w, for a maximum of 32 doses or 96 weeks of therapy, whichever comes first.

Cohort 1B: During BCG Induction Course (12 weeks), patients receive atezolizumab 1200 mg IV q3w for a total of four doses. During BCG Maintenance Course 1 (12 weeks), patients will receive atezolizumab 1200 mg IV q3w for a total of four doses. Additional BCG maintenance courses are not required for patients in Cohort 1B, but may be permitted following discussion with the Medical Monitor. During BCG Maintenance Courses 2–5 (each 24 weeks), patients receive atezolizumab 1200 mg IV q3w for a total of eight doses per course. Patients who stop BCG maintenance at any time may continue atezolizumab 1200mg IV q3w. The maximum atezolizumab treatment duration is 96 weeks. Atezolizumab may be administered before or after intravesical BCG on

days when these infusions coincide, however both the atezolizumab infusion and intravesical BCG infusion must be completed within 24 hours of one another.

Cohorts 2 and 3: During BCG Induction Course (12 weeks), patients receive atezolizumab 1200 mg IV q3w for a total of four doses. During BCG Maintenance Course 1 (12 weeks), patients will receive atezolizumab 1200 mg IV q3w for a total of four doses. During BCG Maintenance Courses 2–5 (each 24 weeks), patients receive atezolizumab 1200 mg IV q3w for a total of eight doses per course. Patients who stop BCG maintenance at any time may continue atezolizumab 1200mg IV q3w.

The maximum treatment duration is 96 weeks. Atezolizumab may be administered before or after intravesical BCG on days when these infusions coincide; however, both the atezolizumab infusion and intravesical BCG infusion must be completed within 24 hours of one another.

Administration of atezolizumab will be performed in a setting with emergency medical facilities and staff who are trained to monitor for and respond to medical emergencies. For more detailed information regarding administration, refer to the Investigator's Brochure and Pharmacy Manual.

The initial dose of atezolizumab will be delivered over 60 (\pm 15) minutes. If the first infusion is tolerated without infusion-associated adverse events, the second infusion may be delivered over 30 (\pm 10) minutes. If the 30-minute infusion is well tolerated, all subsequent infusions may be delivered over 30 (\pm 10) minutes. For the first infusion, the patient's vital signs (heart rate, respiratory rate, blood pressure, and temperature) should be determined within 60 minutes before, during (every 15 [\pm 5] minutes), and 30 (\pm 10) minutes after the infusion. For subsequent infusions, vital signs will be collected within 60 minutes before infusion and at the end of the infusion. Patients will be informed about the possibility of delayed post-infusion symptoms and instructed to contact their study physician if they develop such symptoms.

No premedication is indicated for the administration of atezolizumab in Cycle 1. Patients who experience an infusion-related reaction with Cycle 1 of atezolizumab may receive premedication with antihistamines or antipyretics/analgesics (e.g., acetaminophen) for subsequent infusions (see [Table 7](#)).

Table 7 Guidelines for the Management of Infusion-Related Reactions during the First Atezolizumab Infusion

Toxicity	Severity	Management
Infusion-related reaction	Grade 1	
 • Reduce infusion rate to half the rate being given at the time of event onset. • After the event has resolved, the investigator should wait for 30 minutes while delivering the infusion at the reduced rate. • If tolerated, the infusion rate may then be increased to the original rate.
	Grade 2	
 • Interrupt atezolizumab infusion. • Administer aggressive symptomatic treatment. • Restart only after the symptoms have adequately resolved to baseline grade. • The infusion rate at restart should be half of the infusion rate that was in progress at the time of the onset of the IRR. • At next cycle, administer oral premedication with antihistamine and anti-pyretic and monitor closely for infusion reaction.
	Grade 3 or 4	
 • Stop infusion. • Proper medical management which may include oral or IV antihistamine, anti-pyretic, glucocorticoids, epinephrine, bronchodilators, and oxygen. • Discontinue atezolizumab. • Contact the Medical Monitor if atezolizumab is discontinued.

For anaphylaxis precautions, see [Appendix 8](#).

The atezolizumab dose may be interrupted for up to 12 weeks for Grade ≥ 3 toxicity or adverse event. If the adverse event does not resolve to Grade ≤ 1 within 12 weeks of last dose of atezolizumab, further treatment with atezolizumab will be discontinued.

There will be no dose reduction for atezolizumab in this study. Patients may temporarily suspend study treatment for up to 12 weeks beyond the last dose if they experience adverse events that require a dose to be withheld. If atezolizumab is withheld because of adverse events for > 12 weeks beyond the last dose, then the patient will be discontinued from atezolizumab treatment and will be followed up for safety and efficacy as specified in Section 4.5.11.

If, in the judgment of the investigator, the patient is likely to derive clinical benefit from atezolizumab after a hold of > 12 weeks, study drug may be restarted with the approval of the Medical Monitor.

If a patient must be tapered off steroids used to treat adverse events, atezolizumab may be held for additional time beyond 12 weeks from the last dose until steroids are discontinued or reduced to prednisone dose ≤ 10 mg/day (or dose equivalent). The acceptable length of interruption will depend on an agreement between the investigator and the Medical Monitor.

Guidelines for treatment interruption or discontinuation and for the management of specific adverse events are provided in Section 5.1.3.

Any overdose or incorrect administration of study drug should be noted on the Study Drug Administration electronic Case Report Form (eCRF). Adverse events associated with an overdose or incorrect administration of study drug should be recorded on the Adverse Event eCRF.

Refer to the pharmacy manual for detailed instructions on drug preparation, storage, and administration.

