- If cytology results are Suspicious or Indeterminate and the biopsies are negative, then treat as if the result was negative
- All occurrences of positive urine cytology will require further evaluation by cystoscopy and/or upper tract imaging. A positive cytology result only indicates presence of disease and cannot be used alone to determine disease progression.

The date of a positive cytology result can be used for the date of recurrence, if the results of the cystoscopy, biopsy, or upper urinary tract assessment shows recurrence.

Patients with persistent and/or recurrent high grade NMIBC without progression (stage or grade progression of active disease, or the presence of new disease) at 12 weeks from treatment initiation may continue on study treatment.

Patients with recurrent low-grade papillary disease will be required to undergo resection with TURBT (unless medically contraindicated) and may continue on study and receive study treatment.

Indications for Discontinuation from Study for Disease Progression

- Stage or grade progression at any timepoint would require discontinuation from study therapy.
- Patients with persistent and/or recurrent high-grade NMIBC (any pT1, high grade pTa, or CIS) on or after the 6-month biopsy will be discontinued from study treatment and offered the option to undergo cystectomy or other bladder-sparing modalities as is clinically appropriate. Patients who undergo cystectomy will be requested to submit additional tissue from their cystectomy specimens.
- Patients with evidence of disease progression to muscle-invasive or metastatic disease at any timepoint will be discontinued from study treatment.

For all patients, additional evaluation (imaging, exam under anesthesia, biopsies) should be performed at investigator discretion for any of the following circumstances:

- Abnormal cystoscopy
- Positive urine cytology
- Two sequential suspicious or indeterminate urine cytology specimens

Study treatment with atezolizumab may be continued for a maximum of 32 q3w cycles or a total of 96 weeks of therapy. BCG treatment (induction and maintenance) may be continued for a maximum of 120 weeks (as clinically indicated; see [Appendix 3](#)). All study treatment will be discontinued in patients who undergo cystectomy or experience disease recurrence/progression or unacceptable toxicity, and in those who are not benefiting from study treatment (in the opinion of the investigator or the patient).

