Notes: Cohort 1B: During BCG Induction Course, patients receive atezolizumab 1200 mg IV q3w for a total of four doses plus BCG at the assigned dose weekly for a total of six doses. During BCG Maintenance Course 1, patients receive atezolizumab 1200 mg IV q3w for a total of four doses plus BCG at the assigned dose weekly for a total of three doses. OPTIONAL BCG Maintenance Courses 2-5, patients receive atezolizumab 1200 mg IV q3w for a total of eight doses per course plus BCG at the assigned dose weekly for a total of three doses per course. An optional collection of biopsy samples at disease progression/disease recurrence will be performed if clinically feasible.

Figure 6 Treatment Plans (cont.)

Cohorts 2 and 3

BCG = bacille Calmette-Guérin.

Notes: Cohorts 2 and 3: During BCG Induction Course, patients receive atezolizumab 1200 mg IV q3w for a total of four doses plus BCG at the assigned dose weekly for a total of six doses. During BCG Maintenance Course 1, patients receive atezolizumab 1200 mg IV q3w for a total of four doses plus BCG at the assigned dose weekly for a total of three doses. During BCG Maintenance Courses 2-5, patients receive atezolizumab 1200 mg IV q3w for a total of eight doses per course plus BCG at the assigned dose weekly for a total of three doses per course.

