Appendix 2 Schedule of Assessments: Cohorts 1b, 2, and 3 (cont.)

Study Procedures	Screening (Days –28 to –1)	Weeks 1–96 ^a	Disease Progression	Treatment Completion/ DC Visit ^b	Follow-Up
HIV, HBV, HCV serology ^q	x				
TB test ^r	x				
Serum pregnancy test ^{n, s}	x	q3w ^f		x	
Archival/screening FFPE tumor tissue specimen or 10 unstained slides ^t	x				
Serum PK sample ^u		See Appendix 5			
Serum ATA sample ^u		See Appendix 5			
Plasma PD Biomarker		See Appendix 5			
Atezolizumab infusion ^v		x			
BCG administration ^w		BCG Induction: weekly for 6 weeks (Weeks 0–11) BCG Maintenance Course 1: weekly for 3 weeks (Weeks 12–23) BCG Maintenance Course 2: weekly for 3 weeks (Weeks 24–47) BCG Maintenance Course 3: weekly for 3 weeks (Weeks 48–71) BCG Maintenance Course 4: weekly for 3 weeks (Weeks 72–95) BCG Maintenance Course 5: weekly for 3 weeks (Weeks 96–120)			
Tissue biopsy (mandatory sample) ^x		Prior to Cycle 9			

Appendix 2

Schedule of Assessments: Cohorts 1b, 2, and 3 (cont.)

Study Procedures	Screening (Days –28 to –1)	Weeks 1–96 ^a	Disease Progression	Treatment Completion/ DC Visit ^b	Follow-Up
Tissue biopsy (optional sample)			x	x	x
Tumor assessment ^y	x	Every 12 weeks following initiation of atezolizumab ^{y, l}		x ^z	x ^z
Patient-reported outcomes ^{aa}		Cycle 1, Day 1, Cycle 2 Day 1, and every 6 weeks thereafter		x	
Concomitant medications ^{bb}	x ^{bb}	x		x	
Adverse events ^{cc}	x ^{cc}	x		x	x
Survival and anti-cancer therapy follow-up assessment ^{dd}					x
Blood samples for pharmacodynamics and biomarkers ^{ee}		See Appendix 5			
Urine samples for biomarker analysis ^{ff}		See Appendix 5			
Whole blood TruCulture		See Appendix 5			
Whole blood FACS		See Appendix 5			

Appendix 2

Schedule of Assessments: Cohorts 1b, 2, and 3 (cont.)

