- ^u See [Appendix 5](#) for a detailed schedule of sample collection timepoints. Plasma PD biomarker, whole blood PBMC, urine biomarker, and whole blood FACS analysis will be performed at disease progression. Post-atezolizumab dose samples should be collected 30 ± 10 minutes after the end of atezolizumab infusion.
- ^v Atezolizumab will be administered by IV infusion. During BCG Induction Course (12 weeks), patients receive atezolizumab 1200 mg IV q3w for a total of four doses.

Appendix 2

Schedule of Assessments: Cohorts 1b, 2, and 3 (cont.)

During BCG Maintenance Course 1 (12 weeks), patients will receive atezolizumab 1200 mg IV q3w for a total of four doses. During BCG Maintenance Course 2–5 (each 24 weeks), patients receive atezolizumab 1200 mg IV q3w for a total of eight doses per course. The maximum treatment duration is 96 weeks or 32 cycles, whichever occurs first.

- ^w BCG will be administered intravesically. During BCG Induction Course (12 weeks), patients will receive BCG at the assigned dose weekly for a total of six doses. During BCG Maintenance Course 1 (12 weeks), patients receive BCG at the assigned dose weekly for a total of three doses. During BCG Maintenance Courses 2–5 (each 24 weeks), patients receive BCG at the assigned dose weekly for a total of three doses per course. In the absence of unacceptable toxicity or compelling evidence of disease progression, patients deriving clinical benefit may be offered continued study treatments for up to 24 months (in total).
- ^x All patients will undergo a mandatory tumor biopsy sample collection at 6 months (prior to Cycle 9 of atezolizumab). Biopsy must be scheduled 14–21 days prior to BCG administration. Fresh tissue biopsies will also be obtained as clinically indicated (e.g., if patient experiences signs of progression). Mandatory fresh tissue biopsies should include any foci of disease (if present) as well as template biopsies obtained from all quadrants of the bladder. Regions of the template biopsies should include the trigone, left lateral wall, right lateral wall, posterior wall, and dome. Bladder Map template ([Appendix 11](#)) should be used to document the approximate size and location of any abnormalities, as well as the approximate location of template biopsies. Additional tissue biopsies may also be obtained over the course of the study to evaluate disease per investigator assessment.

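### For the combination cohorts, the course-by-course text adds up to 40 atezolizumab infusions against a stated cap of 32; BCG carries two different duration limits, and the Appendix 2 assessment column stops where Course 5 begins

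*Combined protocol and SAP*

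**What the plan says.** **Atezolizumab by course.** Section 4.3.2.1 sets out the combination cohorts one course at a time. It assigns four infusions to the 12-week Induction Course and another four to the 12-week Maintenance Course 1. For the later courses it says: "During BCG Maintenance Courses 2–5 (each 24 weeks), patients receive atezolizumab 1200 mg IV q3w for a total of eight doses per course". The synopsis, the Figure 6 notes and the atezolizumab footnotes to Appendices 2 and 3 repeat these counts. The Figure 6 notes give them without a maximum: "patients receive atezolizumab 1200 mg IV q3w for a total of eight doses per course plus BCG at the assigned dose weekly".

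**Atezolizumab maximum.** Section 3.1.2 says: "Study treatment with atezolizumab may be continued for a maximum of 32 q3w cycles or a total of 96 weeks of therapy". The same limit stands in the synopsis, in the cohort descriptions of Section 3.1.1 and in the footnotes to Appendices 2 and 3. The Appendix 3 calendar shows Cycle 32 at Week 93 and no infusion after it.

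**BCG.** Section 3.1.2 says: "BCG treatment (induction and maintenance) may be continued for a maximum of 120 weeks". The BCG footnote to Appendix 2 (footnote w) says: "patients deriving clinical benefit may be offered continued study treatments for up to 24 months (in total"). Appendix 3 places the three Course 5 instillations at Weeks 96, 97 and 98.

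**Assessments.** The on-treatment column of Appendix 2 is headed Weeks 1–96, but its BCG row assigns Course 5 to Weeks 96–120. Footnote f ties hematology, chemistry, vital signs, performance status and the limited examination to Day 1 of each atezolizumab cycle.

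**The concern.** The course text and the maximum are both instructions to sites, and they disagree about whether atezolizumab is given during Course 5: eight doses in one place, none in the other. The course count appears in several places, so this is not a single slip. Section 4.5.9 also describes one 24-week schedule covering atezolizumab and Maintenance Courses 2–5 together, which encourages the longer reading.

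The consequences fall late in treatment. Section 6.2 promises a summary of study treatment administration, and the planned number of infusions is its natural denominator. A patient who receives all 32 infusions has had 100% of plan under the cap but 32/40 = 80% under the course text. Whether a Cycle 33 infusion is a protocol deviation depends on the page consulted. The adverse-event windows of 30 and 90 days run from the last dose of either drug, so they move with the date on which treatment ends.

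The two BCG limits raise a similar question for patients whose treatment slips. The plan foresees this: it allows toxicity holds, requires BCG to be withheld during systemic corticosteroids, and permits a 28-day vacation delay in the combination cohorts.

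**Working it through.** **1. Reproduce the cap.** At one infusion every 3 weeks, 96 / 3 = 32 cycles. Cycle k falls on Week 3(k − 1), so Cycle 32 falls on Week 3 × 31 = 93. This agrees with the Appendix 3 calendar, so the cap and the calendar are consistent with each other.

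**2. Sum the course text** (inputs from Section 4.3.2.1; BCG counts from Section 4.3.2.2).

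| Course | Weeks | Atezolizumab | Cumulative atezolizumab | BCG | Cumulative BCG |
|---|---|---|---|---|---|
| Induction | 0–11 | 4 | 4 | 6 | 6 |
| Maintenance 1 | 12–23 | 4 | 8 | 3 | 9 |
| Maintenance 2 | 24–47 | 8 | 16 | 3 | 12 |
| Maintenance 3 | 48–71 | 8 | 24 | 3 | 15 |
| Maintenance 4 | 72–95 | 8 | 32 | 3 | 18 |
| Maintenance 5 | 96–119 | 8 | 40 | 3 | 21 |

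Total infusions: 4 + 4 + 4 × 8 = 40. Total duration: 12 + 12 + 4 × 24 = 120 weeks.

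**3. Compare.** 40 − 32 = 8 infusions, and 8/32 = 25% above the cap. Induction through Maintenance 4 already gives exactly 32 infusions in 96 weeks. The excess is therefore Course 5 alone: Cycles 33 to 40, Week 96 to Week 3 × 39 = 117.

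**4. Effect on the date of last dose, with no delays.** Under the cap, the last study dose for a patient who completes Course 5 is BCG at Week 98. Under the course text it is atezolizumab at Week 117. The difference is 117 − 98 = 19 weeks, and the 30- and 90-day windows would shift by the same amount.

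**5. BCG limits.** 24 months = 24 × 365.25 / 12 / 7 = 104.4 weeks. The gap from 120 weeks is 120 − 104.4 = 15.6, about 16 weeks. The scheduled Course 5 instillations at Weeks 96, 97 and 98 lie inside both limits, so scheduled BCG is 6 + 3 + 4 × 3 = 21 instillations under either.

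**6. Assessment column.** If atezolizumab stops at Cycle 32, the last visit that triggers the footnote f assessments is Week 93. Appendix 2 then schedules none of them before the instillations at Weeks 96 to 98. Section 4.5 nevertheless requires a toxicity assessment, with acceptable local laboratory values, before every dose of either drug.

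**The case against.** The best defence is that an explicit maximum governs a general rate. Eight infusions per course is what 3-weekly dosing gives in 24 weeks, the cap stands beside or close to most statements of the counts, and the week-by-week calendar stops at Cycle 32. A careful reader would stop there. This defence stands as mitigation: the contradiction can be resolved by reading several places together. It does not remove the contradiction, because the course text says what patients receive in Course 5 and the calendar shows nothing there. The bare Figure 6 notes are weaker evidence. The graphic could not be read in the text reviewed, and Section 3.1.2, which contains the figure, states the cap.

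A reader might also infer that BCG is capped at 96 weeks, because the Cohorts 2 and 3 paragraph of Section 4.3.2.1 gives a 96-week maximum without naming a drug. That would exclude Course 5 BCG, cut instillations from 21 to 18 and widen the spread of BCG limits to 120 − 96 = 24 weeks. The documents do not support this. The sentence sits under the atezolizumab heading, the parallel Cohort 1B sentence names atezolizumab, and so does the synopsis version of the Cohorts 2 and 3 paragraph. The separate BCG section, 4.3.2.2, has no such limit. The sentence is ambiguous, but it is not a BCG cap. Nor does it follow that exposure to both drugs in Course 5 is undefined: the BCG calendar is definite.

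On assessments, Appendix 3 does schedule cystoscopy and cytology at Weeks 94 and 108, and Appendix 2 has a treatment completion visit within 30 days of the last dose. Course 5 is therefore not left unmonitored. The gap is confined to the scheduled pre-dose safety checks.

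Finally, BCG Courses 2–5 are optional in Cohort 1B, so some patients will never reach the conflict.

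**Conclusion.** The point holds for atezolizumab without further assumptions: 40 infusions by course text against 32 by cap and calendar, with all 8 of the difference in Course 5. For BCG it holds in a narrower form: two express limits, 120 weeks and about 104 weeks, which agree on the nominal schedule and part only for a patient delayed beyond 24 months. That figure assumes calendar months converted to weeks. The Appendix 2 column is a scheduling gap against the plan's own pre-dose requirement in Section 4.5.

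Everything here begins at Week 93 or later. It would be wrong to infer an effect on the 6-month CR endpoint, the Day 1–21 DLT window or the precision tables in Section 6.1. The shifts in last-dose date and in the exposure denominator show what would follow if a site acted on the course text; nothing in the documents shows that any site did. The point should be corrected because it concerns treatment instructions and the correction is easy. It does not threaten the main analysis.

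**What to change.** Reconcile the synopsis, Sections 3.1.2 and 4.3.2.1, the Figure 6 notes and Appendices 2 and 3 so that:

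- the per-course atezolizumab counts agree with the stated cap, including an explicit entry for Course 5;
- each drug has one maximum duration, given by name, wherever a maximum appears. This covers the unnamed 96-week sentence in Section 4.3.2.1 and the 24-month limit in Appendix 2 footnote w;
- the Appendix 2 assessment column covers every week in which either drug is scheduled, with pre-dose checks tied to BCG visits as well as atezolizumab cycles where Section 4.5 requires them.

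The sponsor must state which figures are intended; this review takes no position on the treatment rule. The cost is protocol wording and one schedule column, with no change to the sample size or the planned analyses.

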IRRs are known to occur with the administration of monoclonal antibodies and have been reported with atezolizumab. These reactions, which are thought to be due to release of cytokines and/or other chemical mediators, occur within 24 hours of atezolizumab administration and are generally mild to moderate in severity.

CRS is defined as a supraphysiologic response following administration of any immune therapy that results in activation or engagement of endogenous or infused T cells and/or other immune effector cells. Symptoms can be progressive, always include fever at the onset, and may include hypotension, capillary leak (hypoxia), and end-organ dysfunction (Lee et al. 2019). CRS has been well documented with chimeric antigen receptor T-cell therapies and bispecific T-cell engager antibody therapies but has also been reported with immunotherapies that target PD-1 or PD-L1 (Rotz et al. 2017; Adashek and Feldman 2019), including atezolizumab.

There may be significant overlap in signs and symptoms of IRRs and CRS, and in recognition of the challenges in clinically distinguishing between the two, consolidated guidelines for medical management of IRRs and CRS are provided in [Table 7](#).

Appendix 12
Risks Associated with Atezolizumab and Guidelines for Management of Adverse Events Associated with Atezolizumab (cont.)

Table 7 Management Guidelines for Infusion-Related Reactions and Cytokine-Release Syndrome

Event	Management

Grade 1^a Fever^b with or without constitutional symptoms
	
 • Immediately interrupt infusion. • Upon symptom resolution, wait for 30 minutes and then restart infusion at half the rate being given at the time of event onset. • If the infusion is tolerated at the reduced rate for 30 minutes, the infusion rate may be increased to the original rate. • If symptoms recur, discontinue infusion of this dose. • Administer symptomatic treatment,^c including maintenance of IV fluids for hydration. • In case of rapid decline or prolonged CRS (>2 days) or in patients with significant symptoms and/or comorbidities, consider managing as per Grade 2. • For subsequent infusions, consider administration of oral premedication with antihistamines, anti-pyretics, and/or analgesics, and monitor closely for IRRs and/or CRS.

Appendix 12

Risks Associated with Atezolizumab and Guidelines for Management of Adverse Events Associated with Atezolizumab (cont.)

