- ^b Fever is defined as temperature ≥ 38 °C not attributable to any other cause. In patients who develop CRS and then receive anti-pyretic, anti-cytokine, or corticosteroid therapy, fever is no longer required when subsequently determining event severity (grade). In this case, the grade is driven by the presence of hypotension and/or hypoxia.
- ^c Symptomatic treatment may include oral or IV antihistamines, anti-pyretics, analgesics, bronchodilators, and/or oxygen. For bronchospasm, urticaria, or dyspnea, additional treatment may be administered as per institutional practice.
- ^d Low flow is defined as oxygen delivered at ≤ 6 L/min, and high flow is defined as oxygen delivered at > 6 L/min.
- ^e There are case reports where anti-cytokine therapy has been used for treatment of CRS with immune checkpoint inhibitors (Rotz et al. 2017; Adashek and Feldman 2019), but data are limited, and the role of such treatment in the setting of antibody-associated CRS has not been established.
- ^f Resumption of atezolizumab may be considered in patients who are deriving benefit and have fully recovered from the event. Patients can be re-challenged with atezolizumab only after approval has been documented by both the investigator (or an appropriate delegate) and the Medical Monitor. For subsequent infusions, administer oral premedication with antihistamines, anti-pyretics, and/or analgesics, and monitor closely for IRRs and/or CRS. Premedication with corticosteroids and extending the infusion time may also be considered after consulting the Medical Monitor and considering the benefit–risk ratio.
- ^g Refer to Riegler et al. (2019) for information on experimental treatments for CRS.

Appendix 12

Risks Associated with Atezolizumab and Guidelines for Management of Adverse Events Associated with Atezolizumab (cont.)

PANCREATIC EVENTS

Symptoms of abdominal pain associated with elevations of amylase and lipase, suggestive of pancreatitis, have been associated with the administration of atezolizumab. The differential diagnosis of acute abdominal pain should include pancreatitis. Appropriate work-up should include an evaluation for ductal obstruction, as well as serum amylase and lipase tests. Management guidelines for pancreatic events, including pancreatitis, are provided in [Table 8](#).

Table 8 Management Guidelines for Pancreatic Events, Including Pancreatitis

Event	Management

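### A febrile Grade 1 reaction at the first atezolizumab infusion is slowed under Section 4.3.2.1 but stopped under Appendix 12, and nothing says which table prevails

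*Combined protocol and SAP*

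**What the plan says.** Two current tables, both numbered Table 7, tell the site how to handle a mild infusion-related reaction.

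- **Section 4.3.2.1, Table 7.** Its title limits it to the first infusion: "Guidelines for the Management of Infusion-Related Reactions during the First Atezolizumab Infusion". The Grade 1 row begins "Reduce infusion rate to half the rate being given at the time of event onset" and continues: "After the event has resolved, the investigator should wait for 30 minutes while delivering the infusion at the reduced rate". If that is tolerated, the original rate may be resumed. Interruption first appears in the Grade 2 row. The table does not mention CRS and names no grading scale.
- **Appendix 12, Table 7.** The introductory text says that "consolidated guidelines for medical management of IRRs and CRS are provided in" this table. Grade 1 is fever, with or without constitutional symptoms. The actions begin "Immediately interrupt infusion" and then "Upon symptom resolution, wait for 30 minutes and then restart infusion at half the rate being given at the time of event onset". The original rate may be resumed after 30 minutes tolerated at half rate, and that dose is abandoned if symptoms come back.

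Section 5.1.3 sends the reader to Section 4.3.2.1 for infusion-related reactions and to Appendix 12 for immune-mediated events. Section 5.1.1 lists infusion-related reactions among the risks of atezolizumab and refers to Appendix 12 for the detailed description of risks.

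**The concern.** Whether to stop a running infusion is a bedside safety instruction, and here the answer depends on which Table 7 the site opens. Appendix 12 explains why early fever deserves care. Of CRS it says: "Symptoms can be progressive, always include fever at the onset". It also accepts that infusion-related reactions and CRS are hard to tell apart clinically. A mild fever during the first infusion is therefore the moment at which the instruction should be clear.

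A site that follows Section 5.1.3 arrives at the table that keeps the drug running. It also misses two further Grade 1 safeguards that stand only in Appendix 12: abandoning that dose if symptoms return, and considering Grade 2 management if the patient worsens quickly or CRS lasts more than 2 days.

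**Working it through.** No arithmetic applies to the conflict itself. The check sets the two tables side by side and then asks whether any text removes the clash.

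| | Section 4.3.2.1, Table 7 | Appendix 12, Table 7 |
|---|---|---|
| Scope | First infusion only | Infusion-related reactions and CRS; no infusion excluded |
| Grade 1, first action | Halve the rate, keep infusing | Stop |
| Grade 1, after resolution | 30 more minutes at half rate | 30 minutes with no drug, then restart at half rate |
| Grade 1, return to original rate | If tolerated | If tolerated for 30 minutes at half rate |
| Grade 1, symptoms recur | Not addressed | Abandon this dose |
| Grade 2, first action | Interrupt | Interrupt |
| Grades 3 and 4 | Discontinue atezolizumab | Discontinue atezolizumab |

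1. **Do the tables overlap in time?** Yes. The Appendix 12 section opens with premedication at Cycle 1, and nothing in it confines the table to later infusions.
2. **Do they overlap in grade?** Only for part of the reactions. Appendix 12 manages by ASTCT grade (Table 7, footnote a). Section 5.3.3 grades adverse events by NCI CTCAE v4.0. The clash needs a reaction that is Grade 1 under both tables, with fever of at least 38 °C that is "not attributable to any other cause" (footnote b).
3. **Does any text rank them?** No. The Section 5.1.3 pointer is a cross-reference. The summary of changes reports that the infusion-reaction guidance in Appendix 12 was extended to CRS, but does not say that it replaces the body table. Both tables are current text, so this is not a comparison with superseded wording.
4. **How many infusions are exposed?** One per patient out of at most 32 (1/32 = 3.1%). With planned enrolment of up to about 70, that is at most about 70 × 1 = 70 first infusions. The documents give no rate of febrile Grade 1 reactions and do not say how many first infusions remain to be given. The number affected is therefore unknown and may be 0.
5. **Does anything statistical depend on it?** No. Section 3.1.4 counts non-haematologic toxicities as dose-limiting from Grade 3 (Grade 2 for visual changes), so a Grade 1 infusion reaction cannot qualify. A pause within one infusion is far short of the 7-day atezolizumab delay that makes a patient non-evaluable under Section 3.1.3. Reported severity follows CTCAE v4.0 whichever table is used for management.

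**The case against.** The strongest reply is that the site is not left without direction. Section 5.1.3 sends infusion-related reactions to Section 4.3.2.1 and describes Appendix 12 as additional guidance. That stands as a route, but it is not a precedence rule, because Appendix 12 independently directs the same reactions to its own table.

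A second reply is that the overlap may be empty. The CTCAE definition of a Grade 1 infusion reaction is not in the documents. Table 9, which serves events that CTCAE does not list, places minimal non-invasive intervention at Grade 2. If CTCAE draws a similar line (an assumption), a fever that needs treatment would be Grade 2, and both tables interrupt. This limits the size of the problem. It does not make the two Grade 1 rows agree.

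A third reply is that the consequence is small, and this is right. Both paths use half rate and allow a return to the original rate. Both tables are guidelines, and the body table does not forbid stopping. Temperature is taken every 15 (±5) minutes during the first infusion, and staff trained for emergencies are present.

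A reader might go further and infer a three-way conflict, because the fever rows of Table 8 in Section 5.1.3 continue or withhold atezolizumab according to a 38.3 °C threshold. The documents do not support that reading. Section 5.1.3 introduces Table 8 for fever, local bladder symptoms and influenza-like illness that may arise from or be worsened by the BCG combination, and it routes infusion-related reactions elsewhere. The fever rows concern withholding treatment and looking for infection. They say nothing about the rate or interruption of a running infusion.

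**Conclusion.** The plan is wrong as written on this point, as an internal inconsistency, and the matter is minor. For a febrile first-infusion reaction that is Grade 1 under both tables, one instruction keeps the drug running and the other stops it, with no rule of precedence. The textual difference is certain. Whether any patient falls in the overlap is not, because that depends on a CTCAE definition and a reaction rate that the documents do not give. At Grade 2 both tables interrupt, and at Grades 3 and 4 both discontinue, so the stop-or-continue conflict is confined to Grade 1.

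A reader might also infer that the safety evaluation or the dose decision is compromised. It is not: no dose-limiting toxicity, endpoint or analysis is affected.

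**What to change.** Make three changes of wording:

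1. Replace the Grade 1 row of Table 7 in Section 4.3.2.1 with the Appendix 12 Grade 1 action, for any Grade 1 reaction, febrile or not: interrupt; wait 30 minutes after resolution; restart at half rate; return to the original rate if half rate is tolerated for 30 minutes; abandon that dose if symptoms recur.
2. State that Appendix 12 Table 7 prevails wherever the two tables differ.
3. Add Appendix 12 to the infusion-reaction cross-reference in Section 5.1.3.

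Applying the row to all Grade 1 reactions is simpler than splitting management by fever or its cause. In Cohorts 1B, 2 and 3, BCG and atezolizumab that fall on the same day must be completed within 24 hours of each other. Section 5.1.2.1 requires disseminated BCG infection to be ruled out before flu-like symptoms are attributed to atezolizumab. That cannot be settled while an infusion is running. Table 8 needs no change.

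The cost is amendment wording, with IRB/EC approval and regulatory approval where locally required (Section 9.7). Clinically, it is a short pause for a few patients with mild first-infusion reactions. A patient whose symptoms recur would receive only part of that dose, as Appendix 12 already directs for febrile reactions.
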